2.3 Medical Administration

Subjects will be prescribed lisdexamfetamine (LDX) 20mg capsules or a look-alike placebo (microcellulose) by the study PI ([name], M.D.) or her designee. Subjects will be instructed to take one pill (LDX = 20 mg) each morning for 7 days and then will be asked to increase to two pills (LDX = 40 mg) each morning for 14 days. If the study drug is well tolerated by the end of week 3 (as per medication monitoring by the CRC), participants will be asked to increase to three pills (LDX = 60 mg) each morning until the completion of the trial. Participants will be instructed to contact the study team if they experience any side effects and may decrease their medication as instructed. At the end of week 6, which is the end of the trial, participants will be evaluated and instructed to stop their study drug. After an approximate 2-week washout, participants will be crossed over to the other condition and the procedure will repeat. See table below for dosing instructions when the substance is well tolerated.

Week	1	2	3	4	5	6
Dosage	20mg	40mg	40mg	60mg	60mg	60mg

2.4 Medication Dispensation

Subjects will receive one medication bottle at their Trial A Baseline MRI Scan (Visit 2), which should last through the entirety of Trial A (6 weeks). Upon completion of their End of Trial A MRI Scan (Visit 4), subjects will receive their second medication bottle for Trial B. Subjects will be instructed to begin taking the medication after their Trial B Baseline Visit.

In the event that a subject would require additional capsules, another prescription will be submitted on her behalf for the exact number of capsules needed to get her through the remainder of her trial.

2.5 Compensation

Participants will be compensated for their participation in all study visits. If the participant completes all parts of the study, is on time for appointments, and takes her medication, total payment for participants is \$650.

The breakdown of subject payment by visit is as follows:

Visit Name	Visit Number	Amount
Screening Visit*	Visit 1	\$50
Trial A		
Baseline (with Scan)	Visit 2	\$150
Week 3*	Visit 3	\$50
End of Trial A (with Scan)	Visit 4	\$150
Trial B		
Baseline (without Scan)*	Visit 5	\$50
Week 3*	Visit 6	\$50
End of Trial B (with Scan)	Visit 7	\$150

Note: “” indicates that study visit can be complete remotely.*

Subject reimbursement is available for:

- Transportation to and from required in-office visits (Visits 2, 4, and 7).

- Hotel accommodations provided by the research team for up to two nights for required in-office visits (Visits 2, 4, and 7)
- Study-related procedures completed with the subject's physician that were NOT covered by the subject's insurance (i.e., EKG, blood work, and physical exam).

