Remote Baseline (Visit 2): Upon completion of the screening process, subjects will be scheduled for the baseline visit which will require approximately two hours. Medication will be mailed directly to the patient's home through appropriate and approved direct-to-patient services. Subjects will be prescribed study drug for the entirety of Trial A (either placebo or LDX) and instructed to begin taking the medication as directed by the study provider. If the participant needs additional study drug in order to complete the trial an additional script will be submitted to IDS for dispensation. The subject will be sent a scale (if needed) and blood pressure cuff for future remote vital sign collections. On the day of the remote baseline visit, subjects will meet remotely with a member of the study team to complete behavioral assessments regarding their mood and emotions and complete cognitive testing.

Week 2 Phone Check-In: At the end of week 2 of medication use, the CRC will check in with the participant by phone to assess for side effects. Subjects who are having more than mild side effects will be instructed to reduce their dose back to one pill per day.

Week 3 Mid-Trial Check-In: Halfway through Trial A, during their third week, subjects will be scheduled for a remote follow-up visit where they will be monitored by the CRC for potential side effects of the medication and medication compliance. If no or mild side effects are reported, subjects will be instructed to increase the study drug to three pills per day. Subjects who are having more than mild side effects will be instructed to reduce their dose back to one pill per day. The study CRC can exercise her discretion regarding medical personnel involvement at this check-in. Subjects will be instructed to complete various mood and symptoms ratings during the visit. In total, the visit will require approximately 60 minutes and will include measures of blood pressure, pulse, and weight.

Week 4 Phone Check-In: During week 4, the CRC will check in with the participant by phone to assess for side effects. Subjects who are having more than mild side effects will be instructed to reduce their dose back to 2 pills per day for the remainder of the trial.

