5.4 Data Safety and Monitoring

The Principal Investigator (Dr. [name]) will be the primary source for data and subject safety monitoring. The research staff will meet weekly to discuss recruitment, retention, breaches of confidentiality, adverse events, and collected data. Subjects will be instructed to call study personnel as soon as possible in the event of side effects. If we have concerns about their physical and emotional health, we will share these concerns with the subjects' primary care physicians.

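### Section 2.5 makes the full $650 conditional on taking study drug, while its own visit table pays the whole $650 for attendance; the conflict gives a woman a possible reason not to report stopping or side effects

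*Combined protocol and SAP*

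**What the plan says.** Section 2.5 opens with a rule based on attendance: "Participants will be compensated for their participation in all study visits". It then sets three conditions for the total: "If the participant completes all parts of the study, is on time for appointments, and takes her medication, total payment for participants is" $650. A table follows, introduced by "The breakdown of subject payment by visit is as follows". It has seven lines, one per visit, and none for medication.

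Section 2.1 describes how the study learns about tolerability and adherence. At the remote week 3 visit the woman is "monitored by the CRC for potential side effects of the medication and medication compliance", and the next dose step depends on her account: "If no or mild side effects are reported, subjects will be instructed to increase the study drug to three pills per day". The week 2 and week 4 side-effect checks are by phone. Section 2.3 likewise ties the step to the coordinator's monitoring, and adds: "Participants will be instructed to contact the study team if they experience any side effects and may decrease their medication as instructed". Section 5.4 says: "Subjects will be instructed to call study personnel as soon as possible in the event of side effects".

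On drug return, section 2.1 has imaging participants bring back unused capsules and bottles after their last scan. Remote participants return them after each trial (sections 2.1 and 11.4).

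**The concern.** The sentence and the table in section 2.5 give different answers for a woman who keeps every appointment but is no longer taking study drug. No other section settles which applies, and none says that stopping leaves payment intact. Section 3.5, on undue influence, gives assurances about care, employment and education, but not about payment after stopping drug.

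This matters because the plan depends on candour. The dose step turns on the side effects she reports, and compliance is checked by the coordinator at a remote visit. A woman who reads the sentence literally may think that admitting she has stopped, or describing side effects that would lead her to stop, could cost her money. That works against section 5.4, which wants problems reported quickly. It could also make the record of who took the drug less reliable, and the analysis plan in section 4.1 has no adherence variable through which this would show.

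**Working it through.** **1. Reproduce the stated total.** From the section 2.5 table: Visit 1 $50, Visit 2 $150, Visit 3 $50, Visit 4 $150, Visit 5 $50, Visit 6 $50, Visit 7 $150.

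50 + 150 + 50 + 150 + 50 + 50 + 150 = 650.

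This equals the stated $650. The amount left over for taking medication is 650 − 650 = $0. The medication condition therefore cannot add to what the table grants; if it has any effect, it can only reduce it.

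**2. Bound the amount at stake.** Study drug is first handed out at the end of Visit 2 (sections 2.1 and 2.4), so Visits 1 and 2 come before the first dose: 50 + 150 = $200. The remaining visits carry 50 + 150 + 50 + 50 + 150 = $450, which is 650 − 200.

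- Lower bound: $0, if the table governs.
- Upper bound: $450, if every payment after drug start were withheld. Going beyond this would mean taking back money earned before any drug was dispensed, and nothing in the documents provides for that.

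No deduction, adherence threshold or method of judging the condition is given, so the figure cannot be narrowed further.

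**3. Set the two rules side by side.**

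| Woman attends all seven visits on time and | Visit table pays | Conditional sentence |
|---|---|---|
| takes drug throughout | $650 | promises $650 |
| takes a reduced dose as instructed | $650 | not addressed; most naturally still met |
| skips or stops drug | $650 | does not promise $650 |

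The clear conflict is in the last row.

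**4. Ask what else could reveal that she had stopped.** The week 3 visit records blood pressure, pulse and weight, but the text does not use them to judge adherence. Returned capsules and bottles could be counted, but no count is described. The purpose given is return to the investigational pharmacy, with destruction also mentioned in section 11.4. For imaging participants the return is described only after the last scan. No drug level is described either.

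**The case against.** The best defence is that no penalty is written down. The section opens with payment for visits and the table allocates every dollar to them, so the sentence may simply describe a fully completed course. That reading is reasonable, and it is why the lower bound is $0. It leaves the conflict in place, because a participant given both statements cannot tell which one binds.

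Several stronger readings are tempting, and the documents do not support them.

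- **That the study will pay her less if she admits stopping, or that all $650 is at risk.** No deduction is stated, and $200 is earned before the first dose.
- **That women are paid to stay on drug despite side effects.** The plan invites reports of side effects and provides for dose reduction as instructed. Nothing says a reduced dose forfeits payment. The concern reaches women who skip or stop drug, or who hold back side effects because they expect that to follow.
- **That concealed stopping could never be detected.** Returned capsules allow a count, though none is planned in the text.
- **That power falls by a known amount.** One could assume that 5% to 10% of women conceal stopping LDX and show no effect. The 0.3 SD difference in section 4.2 would become 0.30 × 0.95 = 0.285 or 0.30 × 0.90 = 0.27, and paired t-test power at 88 women would go from 79.5% to 75.3% or 70.7%. Those rates have no source in the documents, and some hidden stopping would occur without the clause. The sum shows dilution from non-adherence in general, not the effect of this wording.
- **That hidden stopping concentrates on LDX, or that BADDs scores are lost selectively.** No figure supports the first. The second assumes the unstated forfeiture, whereas the table pays $150 for each end-of-trial visit, which is a reason to attend.

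The compensation terms for the non-imaging group are in a separate consent form (section 3.7) that is not among the documents. Whether it repeats the condition is unknown.

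**Conclusion.** The point holds as a conflict within section 2.5. One sentence makes full payment depend on taking the medication, while the opening rule and the table pay the same $650 for attendance alone. The sum in dispute is between $0 and $450 per woman, assuming that payments earned before first dispensing are not taken back.

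The consequence is a possible incentive, not a demonstrated one, to withhold information on stopping or side effects from the coordinator, on whose checks the dose step and compliance monitoring rest. A reader might infer a measurable bias in the BADDs comparison or a loss of power, but neither can be derived from the documents and neither is claimed. The wording should be corrected because candid reporting matters for safety here and the clause serves no purpose that the table needs.

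**What to change.** In section 2.5, delete the condition about taking medication. State that each visit payment is made for attendance and does not change if study drug is reduced, skipped or stopped. Check the main consent form and the separate non-imaging form, and align them if they carry the same condition.

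The cost is a wording amendment to the protocol, and to the consent forms where needed. No budget is added, because the visit table already totals $650. The downside is the loss of a nominal adherence incentive. No dose, titration step or clinical rule is touched.

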2.6 Study Duration

We anticipate completion of recruitment within 5 years of study inception. Each subject will spend approximately 4-5 months completing all study related procedures.

3. Subject Selection and Withdrawal

3.1 Target Population

We will recruit 100 women, aged 35 to 58 years old, who have undergone a RRSO within the previous 15 years and are currently reporting impairment in some aspect of their daily function. We anticipate a drop-out rate of 10%. Given that the composition of the proposed study population will reflect the Greater Philadelphia referral base, we will make attempts to enhance the recruitment of minorities, but we are limited by the racial and ethnic make-up of women who typically seek oophorectomy for prevention of breast and ovarian cancer.

3.2 Accrual

We anticipate that we will meet our recruitment goals by working with our longstanding collaborators in the Department of Oncology at Penn and the support group: Facing Our Risk of Cancer Empowered (FORCE) for women who are at genetic risk for breast and ovarian cancer and/or gynecologic cancer survivors. Based on previous recruitment efforts, the organization could provide 30% of our participants from the FORCE membership of 25,000 women. Also, 500 BRCA-1/2 gene carriers are followed yearly at the Basser Center for BRCA at the Abramson Cancer Center and the Basser registry of post-RRSO women includes 1800 individuals. Another 50-60 women undergo RRSO each year at one of the University of Pennsylvania Health System hospitals. Additionally, Philadelphia has several other nationally ranked cancer centers from which we can recruit.

We have found advertisements on the local Philadelphia public radio station (WHYY) to be enormously productive for our menopause studies, yielding 1-2 new qualifying participants with each run. Hence, we plan to advertise on WHYY at least twice a month. Also, we have already conducted an online evaluation of the severity of executive function difficulties among post-RRSO women in the greater tri-state area and were granted IRB approval to re-contact these women to inform them about the proposed study. With access to clinical samples and referrals from FORCE and the Basser Center, we could complete our study enrollment if even 5% of the genetically at-risk population in the area were to meet study criteria and agree to participate.

3.3 Key inclusion criteria

1. Females aged 35 to 58 years;
2. Have undergone risk-reducing bilateral salpingo-oophorectomy (RRSO) within the previous 15 years AND were premenopausal at the time of RRSO;
3. Score of ≥ 20 on the Brown Attention Deficit Disorder Scale (BADDs);
4. Onset of executive function difficulties occurred post RRSO;

5. Clean urine drug screen (nicotine and marijuana are permissible). Potential false positive screenings will be reviewed and exclusionary based on PI discretion;
6. Are fluent in written and spoken English;
7. Are able to give written informed consent (obtained at screening visit);
8. Have a high school diploma or equivalent degree (i.e., GED), as per subject report;
9. *If using aromatase inhibitors or tamoxifen:* Must have been on a stable dose for at least 6 months;
10. *If completing visits remotely:* Must have access to a telecommunications application (i.e., Skype), email, scanner/fax machine, and a private area that enables the protection of participant confidentiality.

3.4 Key exclusion criteria

1. Current untreated psychiatric disorder;
2. Substance use disorder within the previous 3 years;
3. Lifetime history of ADHD or psychotic disorder including bipolar disorder, schizoaffective disorder, and schizophrenia;
4. Lifetime history of stimulant abuse or dependence;
5. Regular use of psychotropic medications except selective serotonin reuptake inhibitors (SSRI), serotonin noradrenergic reuptake inhibitors (SNRI), bupropion, zolpidem, gabapentin, or buspirone;
6. Chemotherapy within the past year;
7. Previous history of sensitivity or adverse reaction to lisdexamfetamine (LDX);
8. History of seizures or unstable medical condition;
9. Known heart disease or clinically significant abnormal electrocardiogram during screening as determined by the study MD;
10. Uncontrolled hypertension;
11. Presence of a metallic implant contraindicative to scanning at the 7T level;
11. Claustrophobia;
12. Consistent systolic blood pressure of >145mm Hg or diastolic blood pressure >90 mm Hg after three readings at time of screening;
13. Known renal impairment and End Stage Renal Disease (ESRD).

Note: Chemotherapy and RRSO are commonly paired as a treatment plan for feminine cancers. Participants who underwent relatively concurrent treatments of chemotherapy and RRSO, such as when chemotherapy immediately precedes RRSO, will be considered by the principal investigator and be included at the PI's discretion.

3.5 Populations vulnerable to undue influence or coercion

University of Pennsylvania students and employees (both of appropriate age and study criteria) and economically disadvantaged persons are welcome to participate in this study. Potential subjects will be provided with information about the study and will have the opportunity to ask questions of study staff prior to signing consent. They will be informed that their decision to participate or decline will not affect their care, or their employment or education (if an employee or student of UPenn). The participants will be appropriately consented and their information will be kept in a locked cabinet, filed by code, in a locked room that only the research study personnel has access to.

3.6 Subject Recruitment

Subjects will be recruited by word of mouth, referrals by collaborators at FORCE, the Basser Center, and other medical practices, flyers/brochures, paid advertisements, and direct calling of qualified, prescreened women who agreed to future contact for the proposed study.

3.7 Non-Imaging Subsection of Participants

Subjects will be evaluated for their eligibility to participate in the full list of protocol procedures. However, there may be some subjects that are not eligible due to MRI incompatibility. Therefore, we will have a subsection of participants who are not eligible to complete the MRI due to having metal in their body, claustrophobia, or handedness, but are still eligible to complete all other study procedures at the PIs discretion. The non-imaging subsection will serve as an alternative for anyone unable or not interested in completing the MRI. This subsection of participants will have to meet all other study criteria in order to be included in this subsection and will be reviewed by the PI. Participants eligible for the non-imaging subsection of this study will receive a separate consent form that details the study procedures, risks/benefits, and compensation.

4 Analysis Plan

4.1 Statistical Analysis

Summaries of each outcome (BADDs scores, performance on the cognitive tasks, Glut, and BOLD signal) under each treatment condition (baseline, LDX, and placebo) will be examined using histograms, boxplots, and normal probability plots. Transformations of the outcomes will be considered as necessary to meet modeling assumptions. General linear regression (mixed models) will be employed to estimate the association between each outcome, treatment condition and cross-over sequence while accounting for the nonzero correlation among the repeated observations within individuals.

Aim 1: Total BADDs score at each time point will be examined for an interaction effect between time (pre vs. post) and treatment (LDX vs. placebo) to assess whether within-subject total BADDs score is significantly reduced post LDX treatment rather than post placebo. Baseline BADDs scores will be dichotomized at the median score and considered as a covariate in the mixed effects models. Additional interaction terms for baseline group by time (pre vs. post) and baseline group by treatment (LDX vs. placebo) will be added to the model to test whether treatment effects differentially affect those with higher baseline scores.

Aim 2: Similar models will evaluate BADDs subscores, cognitive task performance, and L-DLPFC Glut levels. Similar mixed models will assess associations between change in specific BADDs domains with identified deficits in executive function and change in DLPFC Glut levels.

Aim 3: We will quantify associations between baseline percentage BOLD signal change during performance of the n-back (3-back) and L-DLPFC Glut.

Current methods for fMRI analyses are as follows: Functional scans will be realigned, normalized, time-corrected, and spatially smoothed by an 8 mm FWHW Gaussian kernel. The time series will be high-pass filtered to correct for drift across the scan. For blocked designed experiments (3-back), regressors will represent trial conditions; for the event-related design

experiments regressions will represent individual trials and trial outcomes. At the individual level, voxel-wise fixed-effects contrast analyses will be performed for each subject to assess the magnitude of pair wise difference in blood oxygen dependent (BOLD) signal between the emotional and the neutral control condition. At the group-level, a second stage of the process will use a random effects model to create spatial parametric maps (SPM) depicting loci that are active across subjects. Movement parameters derived from the realignment correction (for all six possible directions) will be entered into the design matrix as covariates of no interest. For a priori regions of interests, clusters will be reported if they are significant at $P=0.05$ corrected, using a small volume correction (SVC). Clusters will also be reported if they are significant at a threshold of $P=0.001$, uncorrected, with an extend threshold of 10 voxels. Repeated measures analysis of variance (ANOVA) will then be performed to test the effect of LDX on brain activation patterns and simple effects analyses will reveal overall effects of LDX treatment.

fMRI/MRS Analysis: Percent BOLD signal changes in the left DLPFC will be entered in a correlational analysis with corresponding Glut concentrations. Size and orientation of regions included for analysis of BOLD signal and Glut concentration will be identical. Percent BOLD signal change will be calculated for each regressor of interest and correlation coefficients will be obtained. Voxel wise regression of BOLD signal vs. mean Glut concentration will be performed for each functional voxel.

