End of Trial Scan: After the 6-week period, subjects will be scheduled to undergo their end of Trial A ¹H-MRS and fMRI scan session, which will take approximately 75 minutes. Subjects will be instructed to present to the Penn Center for Women's Behavioral Wellness approximately 2.5 hours before their scheduled scan to complete cognitive testing and behavioral assessments

regarding their mood and emotions. Subjects will then be escorted to the CMROI by the study CRC where they will be scanned and asked to perform a series of tasks assessing their memory and attention. In total, the end of Trial A scan will require approximately 4 hours to complete. The completion of this visit concludes all visits for Trial A. Upon completion of the visit and Trial A, subjects will be given the study drug for the entirety of Trial B (either placebo or LDX) and instructed to begin taking the medication after the washout period, as directed by the study provider.

Following an approximate 2-week washout period, subjects will complete their Trial B Baseline Visit, initiating the start of Trial B and medication usage. With the exception of the first baseline scan and cognitive testing, subjects will undergo the same study procedures for Trial B as they did for Trial A. Subsequent to their last scan, subjects will be required to bring their scales, blood pressure cuffs and unused capsules/empty bottles back to the study team so that they can be returned to Penn Investigational Drug Service (IDS).

The primary investigator and research staff will unblind themselves to the drug treatment that was administered in each trial upon each participant's completion or discharge from the study.

Remote End of Trial Visit: After the 6-week period, subjects will be scheduled to undergo their end of trial visit which will require approximately two hours. On the day of the remote end of trial visit, subjects will meet remotely with a member of the study team to complete behavioral assessments regarding their mood and emotions and complete cognitive testing. The completion of this visit concludes all visits for Trial A. Upon completion of the visit and Trial A, subjects will return the prescription bottle and any remaining study drug from Trial A so that they can be returned to Penn Investigational Drug Service (IDS). At this point, all subjects will be instructed to complete an approximate 2-week wash out period before continuing to Trial B.

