Following an approximate 2-week washout period, subjects will be mailed their prescription for Trial B and complete their Trial B Baseline Visit remotely, initiating the start of Trial B and medication usage. Subjects will undergo the same study procedures for Trial B as they did for Trial A.

At the completion of the remote End of Trial B visit, subjects will be required to bring return the scale (if applicable), blood pressure cuffs and unused capsules/empty bottles back to the study team so that they can be returned to Penn Investigational Drug Service (IDS).

The primary investigator and research staff will unblind themselves to the drug treatment that was administered in each trial upon each participant's completion or discharge from the study.

2.2 *1H-MRS Methods*

All the single-voxel ¹H-MRS experiments to measure glutamate will be performed on a 7.0T whole body MRI scanner (Siemens Medical Systems, Erlangen, Germany) with a vendor supplied volume coil transmit/32 channel receive proton head phased array coil. BOLD signal change will be measured during performance of cognitive task and during rest.

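### The Aim 1 model for total BADDs has no Trial A versus Trial B (period) term; keep the planned contrast and add period-by-time

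*Combined protocol and SAP*

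**What the plan says.** Section 1.2 makes total BADDs the primary outcome. Section 4.1 plans mixed models "to estimate the association between each outcome, treatment condition and cross-over sequence while accounting for the nonzero correlation among the repeated observations" on each woman. Under Aim 1 the plan reads: "Total BADDs score at each time point will be examined for an interaction effect between time (pre vs. post) and treatment (LDX vs. placebo"). Time here means before and after within one six-week trial. Sequence is fixed for each woman, so it cannot stand in for period. No term distinguishes Trial A from Trial B.

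Section 4.2 sizes the study at 88 for a 0.3 SD difference between the changes on LDX and on placebo, which matches the Aim 1 contrast.

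Whether BADDs is scored at the start of Trial B is implied but not stated. In section 2.1, imaging-track women "subjects will complete their Trial B Baseline Visit, initiating the start of Trial B and medication usage", and "With the exception of the first baseline scan and cognitive testing, subjects will undergo the same study procedures for Trial B". For the remote track: "Subjects will undergo the same study procedures for Trial B as they did for Trial A". No visit description names BADDs at the Trial B baseline, and section 4.1 summarises outcomes "under each treatment condition (baseline, LDX, and placebo"), with a single baseline.

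**The concern.** In a two-period cross-over, each woman's LDX-minus-placebo difference contains any difference between the periods, with a sign set by her sequence. With equal numbers per sequence, that difference cancels from the mean but stays in the residual error. With unequal numbers, part of it is read as a drug effect. Balance cannot be taken for granted: the protocol text does not state the allocation ratio between sequences, and section 3.1 expects 10% drop-out. What is at stake is the power, and to a lesser degree the bias, of the primary test.

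**Working it through.** **Inputs from the documents:** two-period cross-over (2.1); BADDs of at least 20 at entry (3.3); 10% drop-out (3.1); 5% alpha, 80% power, 0.3 SD, 88 women (4.2). **Assumed:** delta; the share p of candidates removed by the entry cut; the correlation rw between pre and post scores within a trial; the correlation rb across trials.

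**1. The plan's figure.** n = ((1.960 + 0.842)/0.3)² = 87.2, rounded up to 88. By the paired t test, 88 women give 79.5% power. The figure reproduces.

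**2. What Aim 1 tests.** Let D = (post − pre on LDX) − (post − pre on placebo). In a simulated data set, the fitted time-by-treatment interaction equalled the mean of D exactly (−0.09696), and adding the median-split baseline group did not change it.

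**3. Omitting period.** Scale D to SD 1. Its mean is τ + delta for women taking LDX first and τ − delta for the others. With f the share taking LDX first, the mean over all women is τ + (2f − 1) × delta. At 44:44 the apparent variance of D is 1 + delta², which is 1.09 at delta 0.3 and 1.25 at delta 0.5.
- 44:44: no bias. Simulated power is about 77% at delta 0.3 and 72% at 0.5; with the period difference fitted it returns to about 80%.
- 50:38: 2f − 1 = 12/88 = 0.136. Bias is 0.136 × 0.3 = 0.041 (14% of the 0.3 SD effect) or 0.136 × 0.5 = 0.068 (23%). Simulated type I error lies between 5% and 6.5%. Fitting period removes the bias.

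**4. How large delta might be.** If the qualifying BADDs score also serves as the Trial A baseline, Trial A change contains regression to the mean that Trial B change does not. Then delta = (1 − rw) × φ(z)/(1 − p) ÷ √(4(1 − rw)).
- Low end (p = 10%, rw = 0.9): 0.1 × 0.195 ÷ 0.632 = 0.03.
- High end (p = 50%, rw = 0.7): 0.3 × 0.798 ÷ 1.095 = 0.22.

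Bias at 50:38 is then 0.136 × 0.03 = 0.004 to 0.136 × 0.22 = 0.030, or 1% to 10% of the target effect. At 44:44 and delta 0.22, the effect shrinks to 0.3/√1.048 = 0.293 and power is 77.6%, a loss of about 2 points.

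**5. Form of the term.** An additive period term shifts a trial's pre and post scores equally, so it cancels from D and leaves the bias in place. Only period-by-time enters the contrast. The covariance matters too. A random intercept for woman alone treats all four scores as equally correlated. At rw/rb = 0.8/0.5 the average correlation is (2 × 0.8 + 4 × 0.5)/6 = 0.60, so the model variance is about 4(1 − 0.60) = 1.60, against a true 4(1 − 0.8) = 0.80. A trial-within-woman effect corrects this.

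**6. Adjusting for each trial's baseline.** With b = (rw − rb)/(1 − rb), the change contrast has variance 4(1 − rw) and the adjusted end-of-trial contrast 2(1 − rb)(1 − b²), in units of score variance. The ratio is 2/(1 + b).

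| rw/rb | change | adjusted | ratio | power at 88 |
|---|---|---|---|---|
| 0.9/0.3 | 0.40 | 0.37 | 1.08 | 82% |
| 0.9/0.6 | 0.40 | 0.35 | 1.14 | 84.5% |
| 0.8/0.5 | 0.80 | 0.64 | 1.25 | 87.5% |
| 0.8/0.6 | 0.80 | 0.60 | 1.33 | 89.5% |
| 0.7/0.5 | 1.20 | 0.84 | 1.43 | 91.4% |

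If one baseline serves both trials, it cancels and the ratio is 1.00.

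**7. Carry-over.** Suppose LDX shifts the Trial B baseline by λ and a share q of that remains at the end of Trial B. The change contrast is biased by λ(1 − q)/2 and the adjusted one by λ(b − q)/2. With b from 0.75 down to 0.40 (the last four rows), q = 1 gives 0 against −0.125λ to −0.30λ, and q = 0 gives 0.50λ against 0.375λ to 0.20λ. The ranking reverses with persistence.

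**The case against.** The strongest reply is that nothing in the planned test is broken. It is valid under balance, 88 is right, and deltas of 0.3 and 0.5 have no source in the documents. The only documented mechanism is weak, and it needs the qualifying score to double as the Trial A baseline; section 2.1 describes separate screening and Visit 2 assessments, and a fresh Visit 2 score would absorb much or all of the effect. If 100 women were allocated equally, 50:38 would need all 12 losses to fall in one sequence. All of this stands and limits the size of the point. It does not argue for leaving out a term that costs about one degree of freedom.

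A reader might infer three stronger things.
- **That the baseline-adjusted analysis should become primary.** The documents do not support this. The gain needs a Trial B BADDs score that no section names, its size rests on assumed correlations, and carry-over, on which the documents give no data, decides which contrast is less biased.
- **That listing conditions as baseline, LDX and placebo already delivers that precision through a common baseline mean.** It does so only with a trial-within-woman covariance. With a simple within-woman correlation, that model's LDX-placebo contrast is the raw end-of-trial difference, with variance 2(1 − rb): 0.80, 1.00, 0.80 and 1.00 for the last four rows of the table, against 0.35, 0.64, 0.60 and 0.84 adjusted.
- **That the median split costs precision.** It is there "to test whether treatment effects differentially affect those with higher baseline scores" and leaves the estimate unchanged.

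**Conclusion.** The point holds as a modest gap in the primary model. The absence of a period term is plain from section 4.1. Its consequence depends on delta and on sequence balance, neither of which the documents give. At illustrative deltas of 0.3 and 0.5, power drops to about 77% and 72% when balanced, and bias reaches 0.041 and 0.068 SD at 50:38. Under the entry-cut mechanism alone, the cost is at most about 2 power points when balanced and 0.004 to 0.030 SD of bias at 50:38. A reader might conclude that the primary test is invalid or the sample size wrong; neither follows, since the contrast is valid with balanced sequences and 88 reproduces. The possible gain from baseline adjustment, to roughly 82–91% power under the assumed correlations, is real only if BADDs is scored at both baselines, and it supports a sensitivity analysis rather than a new primary test.

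**What to change.** 1. In section 4.1, keep the Aim 1 time-by-treatment contrast as primary and add period, entered as period-by-time, with random effects for woman and for trial within woman. The cost is about one degree of freedom and a sentence of SAP text.
2. State whether total BADDs is scored at both the Trial A and Trial B baseline visits. If it is, pre-specify as a sensitivity analysis the end-of-trial treatment effect with treatment, period and sequence, adjusted for continuous trial-specific baseline BADDs (the woman's mean plus her within-woman deviation). This costs about two further degrees of freedom in that analysis and needs no new data. If it is not scored at both, add only the period term.
3. Aim 2 says "Similar models will evaluate BADDs subscores, cognitive task performance, and L-DLPFC Glut levels". Limit the amended form to BADDs total and subscores, and specify separate models for Glut (no Trial B baseline scan) and for imaging-track cognitive tasks (no Trial B baseline testing).
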